4.3.3 Background therapy

24h oral **intake of fluid and sodium will be restricted to 1500 mL and 1.5 g**, respectively. It is recommended that all patients receive the same maintenance infusion with 500 mL glucose 5% and 3g MgSO₄ administered over 24h time interval, until complete decongestion or end of the study treatment phase. All non-protocol fluids administered (including those for administration of intravenous medication) should be limited.

In case of **serum potassium levels <4 mmol/L**, 40 mmol of KCl is added to the maintenance infusion. Oral potassium supplements may be used at the discretion of the treating physician, but their use will be prospectively registered.

In case of **metabolic acidosis with serum bicarbonate levels <20 mmol/L**, it is recommended to administer intravenously 100 ml of NaHCO₃ 8.4%.

Treatment with **neurohumoral blockers** (e.g. renin-angiotensin system blockers, sacubitril/valsartan, beta-blockers, and mineralocorticoid receptor antagonists) may be continued at the same or lower dosage at the discretion of the treating physician, until the end of the treatment phase (max 4 days) or until complete decongestion is achieved, whatever comes first. Dose increases for any of these medications are not allowed during the screening and treatment phase with the exception of mineralocorticoid receptor antagonists in case of hypokalemia despite intravenous potassium supplement. In addition, starting an SGLT2 inhibitor and a switch from renin-angiotensin system blockers to sacubitril/valsartan is not allowed during the screening and treatment phase, but might be pursued after decongestion is achieved. After decongestion, it is strongly recommended to up-titrate doses of neurohumoral blockers according to the guidelines in the HFrEF patients. Dosages of neurohumoral blockers are collected at screening, at discharge and at three months follow-up.

4.3.4 Randomisation and blinding

The ADVOR study is a randomized double blind clinical trial with 2 treatment arms; therapy with high-dose loop diuretics and placebo vs therapy with high-dose loop diuretics and acetazolamide. An automated web-based system is used to randomly assign patients in a 1:1 ratio with variable blocks sizes, stratified for LVEF according to study centre. To ensure an equal proportion of HFpEF

versus HFREF patients in both study arms, the population will be stratified at inclusion according to LVEF $\leq 40\%$ versus $>40\%$. Permuted block randomization according to centre and LVEF stratum will be used to achieve this.

Patient, site personnel, sponsor personnel and data analysts will remain blinded to the identity of the treatment from the time of randomization until database lock. Though we do not foresee serious adverse events related to the study drug, the study code should only be broken for valid medical or safety reasons e.g. in the case of a severe adverse event where it is necessary for the investigator or treating health care professional to know which treatment the patient is receiving before the participant can be treated.

Following rules apply for unblinding;

- Rapid unblinding of a patient can be performed by a physician of the study team. Detailed information concerning the unblinding procedures is provided in the Manual of Operations.
- On receipt of the treatment allocation details, the PI or treating health care professional will continue to deal with the participant's medical emergency as appropriate.
- The PI/Investigation team documents the breaking of the code and the reasons for doing so on the medical notes and eCRF. It will also be documented at the end of the trial in any final study report and/or statistical report.

Unblinded data are to be kept strictly confidential until the time of unblinding of the trial and will not be accessible by anyone else involved in the trial with the following exceptions: (1) the Project Manager of the company responsible for the labelling and packaging of the IMP, (2) the IRT system programmers who work on the randomization and drug management system; and (3) the data manager who prepares reports required for regulatory reporting (suspected unexpected serious adverse reactions [SUSAR] reporting). These individuals will not be involved in the day-to-day running of the study.

4.4 Endpoint adjudication

Because the primary endpoint requires physical examination of the blinded study physician, adjudication of the primary event is not possible. However, all admission labelled as HF readmission, all-cause mortality and the need for renal replacement therapy will be adjudicated by the Endpoint Adjudication Committee (EAC)

For the endpoints HF readmission, all-cause mortality and the need for renal replacement therapy a complete endpoint package will need to be send to the sponsor. This package should include anonymized source documents (SDs) relevant to the endpoint reported (e.g. discharge letter, emergency room notes, etc). The SD should include at least the reason for admission/death and the received treatment for the event (if applicable). This package will be assessed by the Endpoint adjudication members of the Endpoint adjudication committee.

In case of discrepancy between the evaluation of the EAC members regarding the same event, the Trial Data Manager will contact the EAC members to inform them on the discrepancies found so the both of them can come to a final decision. The discrepancies and the final decision will be documented.

4.5 Sample Size

The ADVOR study is powered for primary endpoint which is the most relevant endpoint with respect to the study hypothesis and reliable data from large randomized clinical trials are available to make a formal power calculation.

In the DOSE trial, which recruited a similar study population as targeted in the ADVOR study, successful decongestion with a similar definition was approximately 11% vs 18% after 72 h in the low vs high-dose loop diuretics arm. The high-dose loop diuretics arm of the DOSE trial is quite comparable to the standard of care group in the ADVOR study as the loop diuretic dose used in the latter is only slightly lower (2x instead of 2.5x the oral maintenance outpatient dose) and non-loop diuretics, which were infrequently used in the DOSE trial, are not allowed. Because of these slight differences, 15% is chosen as an estimate for occurrence of the primary endpoint in the monotherapy with high-dose loop diuretics (SOC) group.

No reliable data are available from large clinical trials to estimate occurrence of the primary endpoint in the acetazolamide arm of the ADVOR study. Therefore, after thorough discussion with the advisory board a success rate of 25% was chosen, which represents a clear meaningful benefit of 10% more patients with appropriate decongestion after 72 h. Using both estimates, considering a type I error rate $\alpha=0.05$ and type II error rate $\beta=0.20$ (yielding a statistical power of 80%), the targeted sample size for the ADVOR study is calculated at $n = 494$. A 5% drop out has been calculated in order to estimate the total number of 519 patients to be enrolled in the study.

5 STATISTICAL ANALYSIS

5.1 General principles

This statistical analysis plan dated 17 January 2022 is based on the statistical information documented in the study protocol version 2.0 dated 03 January 2019 (see section 10), the methods paper published in the European Journal of Heart Failure (2018)³ and guidance by the European Medicines Agency (EMA)⁴ and the Food and Drug Administration⁵ regarding the management of clinical trials during COVID-19 pandemic (2021).

The scope of this statistical analysis plan is to outline the statistical tools used for the primary and secondary objectives of the ADVOR study following the procedures documented in the study protocol version 2.0 dated 03 January 2019 in all participating centres.

Prior to the statistical analysis the collected study data will be cleaned by the data management team of the Clinical Trial Unit at the Ziekenhuis Oost-Limburg (ZOL-CTU). The cleaning will be performed according to the Data Management Plan agreed for the ADVOR trial.

All statistical hypothesis are 2-sided and a 5% significance level will be used. A correction for multiple testing will not be implemented.

Trial results will be reported according to the CONSORT statement on reporting randomized controlled trials.

For the analysis of the primary outcome, each secondary and exploratory outcome the following information will be presented:

- the number of patients included in each analysis, by treatment arm
- a summary statistic of the outcome (e.g. number (%), mean (SD)), by treatment arm

- the estimated treatment effect
- a 95% confidence interval for the estimated treatment effect
- A two-sided p-value for all analyses, a significance level of 5% will be used.

All statistical analysis will be done with Statistical Analysis System (SAS) for Windows, SAS 9.4.

5.2 Interim analyses

No interim analysis is planned regarding the ADVOR study.

5.3 Multiplicity adjustment

There will be no correction for multiplicity of testing as there is only one primary endpoint. All other endpoints and subgroup analyses will be considered as exploratory.

5.4 Blind review

Once the database is cleaned the dataset will be locked and transferred to an independent academic statistical center (DSI/CenStat - University Hasselt) for efficacy and safety analysis according to the statistical analysis plan

5.5 Data sets to be analysed

For the *primary endpoint* the statistical analysis will be based on an intention-to-treat analysis set (ITTAS) including all randomized patients. Patients will be analysed according to the treatment group they were allocated to according to the electronic randomization system (irrespective of the actual treatment received).

For the *secondary endpoints* the statistical analyses will be based on the same data set as will be used for the primary endpoint analysis.

For the *safety endpoints*, all patients that were randomized and received at least 1 dose of the investigated drug or placebo will be included (safety population). For the safety analysis, patients will be grouped based on the actual study treatment received.

5.6 Subject disposition

After closing of the database, a CONSORT diagram will be produced for transparent status of the subject reporting.

5.7 Violations and deviations

The important protocol deviations listed below will be summarised by randomized treatment group

- Patients who were randomized but did not meet inclusion and exclusion criteria
- Patients who received study treatment with a wrong treatment vial number at any time during the study
- Patients who received only acetazolamide/placebo but no loop diuretics on day 1, 2 or 3

As the primary analysis is an intention-to-treat analysis, protocol deviation will not imply exclusion from the primary analysis.

5.8 Concomitant therapies

The frequency of baseline medication will be shown for the intention-to-treat analysis set (ITTAS) per treatment group, counts and % will be presented grouping the baseline medication per drug classes.

5.9 Baseline characteristics

To describe the study population, characteristics of all the patients in the ITTAS population will be presented. Numbers (%) or means (SD) and medians (IQR) will be given for each treatment group as appropriate.

5.10 Analysis of the primary outcome

5.10.1 Main analysis

The primary statistical analysis in ADVOR will be an intention-to-treat (see section 5.5).

The primary endpoint is a binary outcome with a success defined as decongestion achieved on the morning of day 4 (or earlier) without the need for escalating diuretic strategy (doubling loop diuretic dose, addition of chlorthalidone, or ultrafiltration) during IV diuretic therapy on morning of day 3.

For descriptive purposes, the number (%) of failure and success for the primary outcome will be given per treatment arm.

The treatment effect for this primary outcome will be evaluated by means of a generalized linear mixed model (logistic model⁶⁷). The statistical model will include a fixed treatment effect, and a random centre effect. The results of this model will be presented as an odds-ratio (OR), 95% confidence interval and the associated p value.

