7.6 Screening phase assessments

Screening testing will occur after the consent process has been finalized. The screening data gathering needs to be performed prior to the administration of the study diuretic agents. The following assessments are required and data need to be collected:

- Obtain written informed consent
- Check inclusion and exclusion criteria
- Collect demographics (collect age, gender, race and ethnicity)
- Collect medical history and notification of LVEF
- Collect concomitant medication ([see Appendix 5](#))
- Collect vital signs including body weight, arterial blood pressure and heart rate
- EQ-5D patient questionnaire to be completed by the patient ([Appendix 2 and 3](#))
- Perform volume assessment by the Principal Investigator or a Sub-investigator who has been trained in the study volume assessment. Volume assessment is based on the presence of oedema, ascites, pleural effusion (Figure 3 in section 8).
- Collect blood sample for local laboratory assessment: serum hemoglobin, hematocrit, electrolytes (Na, K, Cl, HCO₃), serum osmolality, serum urea, serum Cr, total protein, serum albumin, Fe, ferritin, TSAT, LDH, troponin, eGFR and plasma BNP or NT-proBNP
 - In a subset of randomized patients participating in the laboratory sub-study blood collected during screening will be shipped to the University Biobank Limburg ([see section 7.10](#))
- Perform pregnancy urine test (applicable for all pre- menopausal women who are not surgically sterile)
- Randomization ([see section 7.3](#))

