If any of these events occur when the patient is judged to be euvolemic, the study treatment is stopped and stopping is not considered a treatment failure.

[figure not shown]
Freedom from volume-overload (i.e. congestion) on the morning of day 4 will be defined as not more than trace oedema, no residual pleural effusion, and no residual ascites (Figure 3)

Figure 3: Volume assessment

OEDEMA	No oedema (score 0)	Trace oedema (pitting disappear immediately) (score 1)	Clear pitting oedema (score 2)	Visual deformation above ankle (score 3)	Visual deformation above knee (score 4)
PLEURAL EFFUSION (to be confirmed by chest X-ray or ultrasound on admission if suspected)	No pleural effusion (score 0)	Minor (non-amendable for puncture) pleural effusion (score 2)		Major (amendable for puncture) pleural effusion (score 3)	
ASCITES (to be confirmed by ultrasound on admission if suspected)	NO ascites (score 0)	Minor ascites, only detected by echography (score 2)		Significant ascites (score 3)	

Succesfull decongestion

Continue IV diurectic therapy

Treatment DOSE ADJUSTMENTS in case of an inappropriate diuretic response

If the total urinary output (see Figure 1 and [Appendix 4](#)) on the morning of day 3 is < 3500 mL and the patient is still volume overloaded, an escalation of decongestive treatment is mandatory. One of the outlined three options can be chosen at the discretion of the treating physician.

Escalation therapy options:

- doubling of the IV dose of the loop diuretics
- add oral chlorthalidone 50 mg once daily
- ultrafiltration or renal replacement therapy might be considered

The decision to proceed with escalation therapy needs to be collected in the case report form as the patient needing escalation cannot reach the primary endpoint.

Background therapy

24h oral intake of fluid and sodium will be restricted to 1500 mL and 1.5 g, respectively. It is recommended that all patients receive the same maintenance infusion with 500 mL glucose 5% and 3g MgSO₄ administered over 24h time interval, until complete decongestion or end of the study treatment phase. All non-protocol fluids administered (including those for administration of intravenous medication) should be limited.

In case of **serum potassium levels <4 mmol/L**, 40 mmol of KCl is added to the maintenance infusion. Oral potassium supplements may be used at the discretion of the treating physician, but their use will be prospectively registered.

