4.1.2 Primary Objective and outcome measure

Primary Objective	Primary Endpoint
To investigate if combination therapy with acetazolamide improves loop diuretic efficacy to increase diuresis in decompensated HF patients with volume overload, allowing for a better/faster decongestion and a lower total dose of loop diuretics.	The proportion of patients achieving decongestion on the morning of day 4 without the need for escalating therapy on the morning of day 3 (treatment success).

Definition of primary endpoint

Congestion is assessed using the **volume assessment score** (also called the congestion score see figure 2). Freedom from volume-overload will be defined as not more than trace oedema, no residual pleural effusion, and no residual ascites (Figure 2).

So a (sum) score ≤ 1 indicates that decongestion is achieved (being dry), a score > 1 is considered to be volume overloaded (decongestion not achieved).

The primary endpoint is a binary endpoint, with a success defined in case of:

- decongestion (volume assessment score ≤ 1) on the morning of day 2
- or decongestion (volume assessment score ≤ 1) on the morning of day 3
- or decongestion (volume assessment score ≤ 1) on the morning of day 4 **without** the need for escalating diuretic strategy on the morning of day 3, which is needed if total urinary output on the morning of day 3 $< 3.5l$ (sum of urinary output from the start of IMP until the morning of day 3).

[figure not shown]

Figure 2. Clinical Congestion Assessment

The SOC therapy results in ~15% effective decongestion¹. It is estimated that the combination therapy should have a success rate of 25%, which represents a clear meaningful absolute benefit of 10% more patients with appropriate decongestion after 72h.

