4.2 Patient population

4.2.1 Inclusion Criteria

- Signed written informed consent must be obtained before any study assessment is performed
- Male or female patients of 18 years of age or older
- An elective or emergency hospital admission with clinical diagnosis of decompensated HF with at least one clinical sign of volume overload (e.g. oedema (score 2 or more), ascites confirmed by echography or pleural effusion confirmed by chest X-ray or echography)
- Maintenance therapy with oral loop diuretics at a dose of at least 1 mg bumetanide or an equivalent dose for at least 1 month before hospital admission (Conversion: 1 mg bumetanide = 40 mg furosemide = 20 mg torsemide)
- Plasma NTproBNP levels >1000 ng/L or BNP levels >250 ng/L at the time of screening
- Assessed LVEF by any imaging technique; i.e. echocardiography, catheterization, nuclear scan or magnetic resonance imaging within 12 months of inclusion

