4.3.1 STOP TREATMENT

The treating physician is allowed (but not obliged) to stop the study treatment, in case of persistent volume-overload in following cases:

- symptomatic hypotension with a systolic blood pressure <100 mmHg
- asymptomatic hypotension with a systolic blood pressure <90 mmHg
- an increase of serum Creatinine levels x 1.5 of the serum Creatinine level compared to admission value
- occurrence of metabolic acidosis (pH < 7.2)

The discontinuation of the study treatment will be seen as a failure for the primary endpoint (decongestion not achieved). However, if any of these events occur when the patient is judged to be euvolemic, the study treatment is stopped and the primary endpoint is considered to be successful (decongestion achieved).

Freedom from volume-overload (i.e. successful decongestion) on the morning of day 4 will be defined as not more than trace oedema, no residual pleural effusion, and no residual ascites (Figure 2).

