4.3.2 Treatment DOSE ADJUSTMENTS in case of an inappropriate diuretic response

If the total urinary output on the morning of day 3 is < 3500 mL and the patient is still volume overloaded, an escalation of decongestive treatment is mandatory. One of the outlined three options can be chosen at the discretion of the treating physician.

Escalation therapy options:

- doubling of the IV dose of the loop diuretics
- add oral chlorthalidone 50 mg once daily
- ultrafiltration or renal replacement therapy might be considered

The decision to proceed with escalation therapy will be collected in the case report as the need for escalation implies a failure for the primary endpoint.

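### The primary model omits the baseline volume score and the LVEF stratum, and the SAP does not carry over the protocol's covariate-extended model; adjusting is a cheap efficiency and robustness gain, not a correction of an error

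*Combined protocol and SAP*

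**What the plan says.** SAP v2.0, 5.10.1, specifies a logistic mixed model for the primary endpoint: "The statistical model will include a fixed treatment effect, and a random centre effect". The result is an odds ratio with its confidence interval and p value.

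SAP 4.3.4 describes the allocation: "Permuted block randomization according to centre and LVEF stratum will be used to achieve this". The strata are LVEF up to 40% and above 40%.

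SAP 4.1.2 rests success on the volume score: "So a (sum) score ≤ 1 indicates that decongestion is achieved (being dry". The score is not the whole endpoint. Escalation counts against the patient, "as the need for escalation implies a failure for the primary endpoint" (4.3.2), and so does stopping treatment while still overloaded: "The discontinuation of the study treatment will be seen as a failure for the primary endpoint (decongestion not achieved" (4.3.1).

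The same score is taken before treatment. Protocol v2.0, 7.6, asks sites to "Perform volume assessment by the Principal Investigator or a Sub-investigator who has been trained in the study volume assessment". SAP Appendix A lists the value as VOA_SCORE_D0.

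Protocol v2.0, 10.3, states among its secondary analyses that the models for the primary and secondary endpoints will be enlarged with covariates. The list is introduced by a phrase that leaves it open. It names sex, age, race, ethnicity, renal function, blood pressure, diuretics and neurohumoral blockers. It names neither LVEF nor the volume score. SAP 5.1 says the SAP is based on protocol section 10, but SAP 5.10 contains no such model.

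**The concern.** One of the two factors that shaped the randomisation is in the primary model and the other is not. The patient's starting point on the scale that largely decides the outcome is also absent. A patient who enters with a score of 2 has less far to go than one who enters with 7, so the baseline score is a natural candidate for a strong predictor. The SAP already follows this principle elsewhere: the quality-of-life model in 5.11.3 includes the baseline value.

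Two things are at stake. The trial is planned at 80% power with little slack, and adjusting for a prognostic baseline raises power and corrects chance imbalance. Second, if the protocol's covariate list stays open, covariates could be chosen after results are seen. That list is not restricted to baseline values, and protocol Appendix 5 has diuretics recorded on treatment days as well as at screening.

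**Working it through.** **1. The plan's own figure.** Inputs from SAP 4.5: 15% against 25%, two-sided 5%, 80% power. With unpooled variance, n per arm = (0.15×0.85 + 0.25×0.75) × (1.960 + 0.842)² / 0.10² = 0.315 × 7.849 / 0.01 = 247.2, or 494.5 in total. This reproduces 494. Then 494 × 1.05 = 519. The crude odds ratio is (0.25/0.75)/(0.15/0.85) = 1.89.

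**2. Does any SAP analysis give one overall adjusted effect on the primary endpoint?**

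| SAP section | Terms beyond treatment and centre | One overall adjusted effect? |
|---|---|---|
| 5.10.1 main | none | no |
| 5.10.2 subgroups | one factor at a time (score split at its median), with treatment interaction | no |
| 5.10.3 missing data | multiple imputation only | no |
| 5.10.4 COVID-19 | period, with treatment interaction | no |

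**3. Range of the score.** From protocol 8.1, Figure 3: oedema 0–4, effusion 0, 2 or 3 ("Minor (non-amendable for puncture) pleural effusion (score 2"), ascites 0, 2 or 3. Entry requires a patient "with at least one clinical sign of volume overload (e.g. oedema (score 2 or more" or with a confirmed effusion or ascites. So the baseline score runs from 2 to 4 + 3 + 3 = 10.

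**4. Simulated power.** Inputs from the documents: n = 494, 15% against 25%, 24 centres, permuted blocks within centre by LVEF stratum. Assumed, because the documents do not give them: the score's prognostic strength and distribution (skewed, mean 4.0, SD 1.6), centre SD 0.5 on the logit scale, LVEF odds ratio 1.35, blocks of 2 or 4. Each scenario had 8,000 trials, a random-intercept logistic fit by maximum likelihood, and a Wald test.

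| Assumed OR per SD of score | Planned model | + LVEF | + LVEF + score | Gain in points over planned model (SE) | Fall in variance of standardised risk difference (SE) |
|---|---|---|---|---|---|
| 1 | 80.6% | 80.6% | 80.7% | 0.1 (0.1) | 0.1% (0.1) |
| 1.5 | 81.2% | 81.4% | 82.1% | 0.9 (0.2) | 1.9% (0.3) |
| 2 | 80.7% | 80.8% | 83.3% | 2.6 (0.3) | 5.8% (0.5) |
| 3 | 80.5% | 80.7% | 85.4% | 4.9 (0.3) | 12.0% (0.7) |

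LVEF alone adds 0.0–0.2 point. Other assumed score shapes gain 2.6–2.8 points at OR 2 and 5.8–6.6 at OR 3; a normal score gives the 6.6, and gives 1.0 at OR 1.5. If the true effect is a step at the median of the same standardised size as OR 2, the linear term still gains 1.3 (0.2). Type I error is 4.5% with and without adjustment.

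**5. Why power rises although the standard error does.** At OR 3 the SE of the log odds ratio goes from 0.237 to 0.256, but the adjusted odds ratio is conditional and moves to a median of 2.13, against 1.92–1.95 unadjusted. The ratios are ln(2.13)/0.256 = 2.95 adjusted, against ln(1.92)/0.237 = 2.75 to ln(1.95)/0.237 = 2.82 unadjusted.

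**6. Second simulation.** Separate code, with no centre variance, a different discrete score, LVEF odds ratio 1.0 or 1.5, and 4,000 runs per scenario. Gains were 0.0 and −0.2 points at OR 1, 0.6 and 0.6 at OR 1.5, 1.9 and 2.4 at OR 2, and 4.6 and 4.4 at OR 3. Adjusted type I error was 4.6–5.6% (simulation SE about 0.3 points).

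**The case against.** The strongest reply is that nothing is broken. The planned test is valid and matches the sample size, and SAP 5.3 rests the claim on one primary endpoint, so a flexible secondary covariate list could not replace the main result. Protocol 10.3 already foresees an adjusted model, and the SAP nowhere withdraws it. The size of the gain is assumed: OR 3 per SD with SD 1.6 means 3^((6−2)/1.6) = 3^2.5, about 16-fold odds of success between scores 2 and 6, and nothing in the documents supports a figure that large. A single linear sum score treats oedema 3, effusion 3 and ascites 3 as equivalent, which was not tested. Changing the primary model now departs from the protocol after the trial was completed (SAP 5.10.4).

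Most of this stands, and it is why the point is optional. What remains is that the SAP is the document that should fix the analysis, and on this model it is silent.

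Three stronger readings do not hold:
- A reader might infer that omitting a stratification factor invalidates the test. It does not: the randomised comparison remains valid, and simulated type I error is 4.5% either way.
- A reader might infer that a model added to 5.10.4 brings the power gain. It does not, because the primary test would be unchanged.
- A reader might infer that a model with LVEF and volume score discharges the commitment in protocol 10.3. It contains none of the covariates named there, so that list needs its own decision.

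**Conclusion.** The gap holds as an opportunity for efficiency and robustness, not as an error. No SAP analysis gives one overall covariate-adjusted effect on the primary endpoint, and the protocol's covariate-extended model has not been carried over or closed.

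The power gain belongs only to a change in 5.10.1 and depends on an assumed prognostic strength: about 0 points if the score is not prognostic, under 1 at OR 1.5 per SD, about 2–3 at OR 2, and about 4–5 at OR 3, with up to 6.6 under other assumed score shapes. There is no material loss if the score proves uninformative. Nearly all of the gain comes from the score; LVEF is included for consistency with the randomisation. A model in 5.10.4 still offers protection against chance imbalance and, if the score is prognostic, a more precise risk difference. Confidence is medium, because prognostic strength, score distribution and centre variance are all assumed.

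**What to change.** Before unblinding, with the date recorded:

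- Add to the 5.10.1 model, as fixed effects without interaction, LVEF stratum (≤40%, >40%) and baseline volume sum score as one linear term. Keep the treatment-plus-centre model as a supportive analysis and document the departure from protocol 10.3 and its synopsis.
- If the sponsor prefers to leave the primary model alone, put the same model in 5.10.4 as a named supportive analysis, and claim no power gain for the primary test.
- In either case, report a standardised risk difference beside the odds ratio, averaged over patients' covariates and the estimated centre distribution, with a delta-method 95% interval (simulated coverage 94.4–95.5%). State how a missing baseline score is handled, for example by the mean over both arms with the number replaced.
- Separately, state whether the covariates listed in protocol 10.3 will be used, at baseline values only, or dropped.

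No new data are needed. The costs are a dated change to the primary model after trial completion (first option only), some extra programming for the risk difference, and an odds ratio that is conditional. Its median was about 1.95 to 2.18 over the scenarios, against a crude 1.89, so it should not be read alone.
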